DESIGN This is a Phase 1/2, randomized, double blind, two-arm, partial cross-over, single-site, pilot study evaluating the effect of oral dipyridamole (DP) on immune activation and inflammation in HIV-1-infected, ART-treated subjects with HIV-1 RNA less than 50 copies/mL. The change from baseline to week 12 in the plasma levels of sCD163 and sCD14, and IL-6 will be assessed within and compared between study arms, as will secondary endpoints related to immune activation, inflammation, gut mucosal changes, pulmonary function and brachial artery flow-mediated dilation (FMD).

Subjects will be randomized 1:1 to DP 100 mg 4 times a day or matching placebo. Following week 12, subjects in the DP arm will continue DP for an additional 12 weeks (for total 24 weeks) and subjects in the placebo arm will cross over to DP 100 mg 4 times a day for 12 weeks.

Evaluations will be scheduled at Entry (week 0) and Weeks 2, 4, 8, 12, 14, 16, 20, 24, and 28.

DURATION Subjects will be in the study for 28 weeks.

[figure not shown]
SAMPLE SIZE 40 subjects, 20 per arm. Rectal Tissue Subset: 20 subjects, 10 per arm.

POPULATION HIV-1-infected male and female subjects, 18 years of age or older, on ART with HIV-1 RNA <50 copies/mL for a minimum of 12 months.

STRATIFICATION Subjects will be stratified by CD4+ T-cell counts (≤ 500 versus > 500 cells/mm³, and by enrollment into the Rectal Tissue Subset)

REGIMEN
Arm A: Dipyridamole 100 mg 4 times daily for 24 weeks
Arm B: Dipyridamole placebo 1 capsule 4 times daily for 12 weeks, then Dipyridamole 100 mg 4 times daily for 12 weeks.

STUDY SCHEMA:

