1.3 Secondary Objectives

1.3.1 To compare changes in the level of T cell immune activation as measured by the proportion of CD8+ and CD4+ T cells co-expressing HLA-DR and CD38 and the proportion of CD8+ and CD4+ T cell co-expressing CD69 and CD25, after 12 weeks of DP treatment to placebo.

1.3.2 To compare changes in cellular markers of monocyte and macrophage activation, as measured by tissue factor and CD16 expression in monocytes after 12 weeks of DP treatment to placebo.

1.3.3 To compare changes in the levels of systemic inflammatory biomarkers (sTNF α R, TNF α , hsCRP) and levels of coagulation (D-dimer, tissue factor) after 12 weeks of DP treatment to placebo.

1.3.4 To compare changes in brachial artery flow-mediated dilation (FMD) 12 weeks after treatment with DP to placebo.

1.3.5 To evaluate the safety and tolerability of DP administered for up to 24 weeks in HIV-1-infected adults.

1.3.6 To assess persistence of changes in immune activation and levels of systemic inflammation, including the primary endpoint measures, after 24 weeks of DP treatment and 4 weeks after discontinuation of therapy.

1.3.7 To assess whether DP reduces the proportion of cycling CD4+ and CD8+ T cells as measured by Ki-67 expression at baseline and after treatment with DP.

1.3.8 To correlate plasma DP levels to urine adenosine, plasma IL-6, and cellular and soluble markers of immune activation.

1.3.9 To evaluate changes in residual plasma HIV-1 RNA using single copy assay (SCA) before and after DP treatment.

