DP has a vasodilatory effect and should be used with caution in patients with severe coronary artery disease (e.g., unstable angina or recently sustained myocardial infarction). Chest pain may be aggravated in patients with underlying coronary artery disease who are receiving DP. Elevations of hepatic enzymes and hepatic failure have been reported in association with DP administration. DP should be used with caution in patients with hypotension since it can produce peripheral vasodilation.

DP has been reported to increase the plasma levels and cardiovascular effects of adenosine and may counteract the anticholinesterase effect of cholinesterase inhibitors, thereby potentially aggravating myasthenia gravis.

Adverse reactions at therapeutic doses are usually minimal and transient. With long-term use of DP tablets, initial side effects usually disappear. The following reactions in Table 1 were reported in two heart valve replacement trials comparing DP tablets and warfarin therapy to either warfarin alone or warfarin and placebo:

Table 1 Adverse Reactions Reported in 2 Heart Valve Replacement Trials

| Adverse Reaction | Dipyridamole Tablets/Warfarin | Placebo/Warfarin |
|-------------------------|--------------------------------------|-------------------------|
| Number of Patients | 147 | 170 |
| Dizziness | 13.6% | 8.2% |
| Abdominal distress | 6.1% | 3.5% |
| Headache | 2.3% | 0.0% |
| Rash | 2.3% | 1.1% |

Other reactions from uncontrolled studies include diarrhea, vomiting, flushing and pruritus. In addition, angina pectoris has been reported rarely and there have been rare reports of liver dysfunction. On those uncommon occasions when adverse reactions have been persistent or intolerable, they have ceased on withdrawal of the medication.

When DP tablets were administered concomitantly with warfarin, bleeding was no greater in frequency or severity than that observed when warfarin was administered alone. In rare cases, increased bleeding during or after surgery has been observed. The

guidelines from the American Society of Gastrointestinal Endoscopy state that low risk endoscopic procedures, including flexible sigmoidoscopy with biopsies, may be performed on patients using standard-dose DP or ASA-DP combinations.⁴³

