3.0 STUDY DESIGN

The proposed study is a randomized, placebo-controlled, two-arm, partial cross-over, single-site, pilot study comparing the effect of 12 weeks of DP or placebo on immune activation and inflammation. The study will enroll approximately 40 HIV-1-infected subjects, age 18 years or older, who have been on ART for at least 12 months prior to study entry and have HIV-1 RNA <50 copies/mL for at least 12 months prior to study entry. Subjects will be randomized equally to two regimens:

Arm A: Dipyridamole 100 mg four times daily for 24 weeks

or

Arm B: Dipyridamole placebo capsule four times daily for 12 weeks, then Dipyridamole 100 mg four times daily for 12 weeks.

Each subject will be enrolled for 28 weeks. Accrual is expected to be completed in approximately 18 months.

In addition, this study will include Rectal Tissue evaluations in 20 subjects (10 per arm). Flexible sigmoidoscopy with biopsies will be done at Entry/Week 0 and Weeks 12, 24, and 28.

The primary endpoints will be change from baseline to week 12 in plasma levels of sCD163, sCD14, and IL-6. Secondary endpoints will include changes in immune activation as measured in blood (%HLA-DR+CD38+CD8+ and CD4+ T-cells and %CD69+CD25+ CD8+ and CD4+ T-cells) and rectal tissue (HLA-DR+CD45RO+CD4+ T-cells, gut-homing CD4+ T-cells), cell-associated HIV-1 RNA and total DNA, and safety and tolerability of DP in HIV-1-infected adults.

Assessment of the primary and secondary endpoints at Week 24 will be conducted to gather additional longitudinal data. Arm A subjects will provide data on the durability of the effect of DP on immune activation, as well as safety and tolerability. Arm B subjects will receive DP from week 12 to week 24 and will enhance the power of the study to detect an effect of DP as well provide additional safety and tolerability data.

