6.0 CLINICAL AND LABORATORY EVALUATIONS

6.1 Schedule of Events (SOE)

| Evaluation | Screening | Pre-Entry ¹ | Entry | Week | | | | | | | | Premature Treatment and/or Study Discontinuation | | |
|--|-----------|------------------------|-------|------|---|---|----|----|----|----|----|--|----|----------------|
| | | | | 2 | 4 | 8 | 12 | 14 | 16 | 20 | 24 | | 28 | |
| Documentation of HIV-1 infection | X | | | | | | | | | | | | | |
| Medical History/Medication History | X | | | | | | | | | | | | | |
| Complete Physical Exam | X | | | | | | | | | | | | | |
| Targeted Physical Exam | | X | X | | X | X | X | | X | X | X | X | | X |
| Clinical Assessments | | | X | | X | X | X | | X | X | X | X | | X |
| Concomitant Medications | | X | X | | X | X | X | | X | X | X | X | | X |
| Hematology | X | | X | | | | X | | | | X | | | X |
| Liver Function Tests/Blood Chemistries | X | | X | | X | | X | | X | | X | | | X |
| Fasting Lipid Panel | | | X | | | | X | | | | X | | | X |
| Plasma HIV-1-1 RNA | X | | X | | | | X | | | | X | | | X |
| CD4+/CD8+ | X | | X | | | | X | | | | X | | | X |
| Pregnancy Test | X | | X | | X | X | X | | X | X | X | X | | X |
| Prothrombin time/INR/PTT ² | | X | | | | | | | | | | | | |
| Hepatitis B and C | X | | | | | | | | | | | | | |
| Stored Plasma for Immunology/Virology ⁵ | | X | X | | X | | X | | X | | X | X | | X |
| Stored PBMC for Immunology/Virology ⁵ | | X | X | | X | | X | | X | | X | X | | X |
| Urine adenosine level (stored) ⁵ | | | X | | X | | X | | X | | X | | | X |
| Serum for Dipyridamole concentration (stored) | | | | | X | X | X | | X | X | X | | | X |
| Brachial Artery FMD | | | X | | X | | X | | | | X | | | X ³ |
| Rectal swabs for GC/CT NAAT ² | X | | X | | | | X | | | | X | X | | |
| HSV Serology ² | | | X | | | | | | | | | | | |
| Flexible sigmoidoscopy (rectal biopsy) ^{2, 5} | | | X | | | | X | | | | X | X | | |
| Adherence self-report | | | | | X | | X | | X | | X | | | |

| Evaluation | Screening | Pre-Entry ¹ | Entry | Week | | | | | | | | Premature Treatment and/or Study Discontinuation | |
|--|-----------|------------------------|-------|------|---|---|----|----|----|----|----|--|----|
| | | | | 2 | 4 | 8 | 12 | 14 | 16 | 20 | 24 | | 28 |
| Medication Adherence Assessment ⁴ | | | X | | X | | X | | X | | X | | |
| Telephone assessment of tolerability/adherence | | | | X | | | | X | | | | | |
| Pre- and post-bronchodilator spirometry ⁶ | | | X | | X | | X | | | | X | | |

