9.6 Secondary Analyses

Changes from baseline to week 12 and week 24 in other secondary and exploratory endpoints including measurements of immune activation, systemic inflammation, and residual virus in blood and rectal tissue, change in pre- and post-bronchodilator FEV₁, and percent FMD (see 9.2.2 and 9.2.3) will be summarized by means, medians, standard deviations, and 95% CIs for each of the treatment arms. As in the primary analysis, between-arm comparisons will be made using either an ANCOVA model or the Wilcoxon rank sum test. For secondary outcomes with more frequent measurements (i.e. baseline, 4, 12 week), longitudinal models such as Generalized Estimating Equations (GEE) will be used to compare the trajectories across time between treatment arms. Included in the model will be predictor variables for week, treatment group, and their interaction.

The study design allows for an additional 12 weeks of follow up in which the placebo arm crosses over to DP 100 mg 4 times daily for 12 weeks. As an exploratory measure, the trajectories of T cell activation and IL-6 expression for these subjects will be analyzed using a generalized linear mixed model with covariates for week (defined as time since initiating placebo/DP), drug (placebo/DP), and their interaction. The effects of long-term and short-term DP on T cell activation will be quantified using an ANCOVA model, similar to the primary analysis.

Safety will be evaluated by summarizing the number and frequency of Grade ≥ 2 adverse events within each study arm. Comparisons between study arms will be done

using Fisher's exact test at each study visit.

Statistical significance for each of the secondary analyses will be tested using the nominal 5% type I error rate.

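### Section 9.6 summarises and tests Grade 2 or higher adverse events by randomised arm with no week-12 limit and never by treatment received, although Arm B starts DP at week 12

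*Combined protocol and SAP*

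**What the plan says.** The safety analysis is two sentences in Section 9.6. The summary sentence reads "Safety will be evaluated by summarizing the number and frequency of Grade ≥ 2 adverse events within each study arm". The next sentence compares the arms "using Fisher's exact test at each study visit". Neither stops at week 12, and Section 9.2.2 attaches no time point to the adverse-event endpoint.

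The synopsis states that after week 12 "subjects in the placebo arm will cross over to DP 100 mg 4 times a day for 12 weeks". Section 3.0 gives a purpose for that period: the Arm B data "will enhance the power of the study to detect an effect of DP as well provide additional safety and tolerability data". Objective 1.3.5 is "To evaluate the safety and tolerability of DP administered for up to 24 weeks in HIV-1-infected adults".

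Section 9.6 does handle the cross-over by drug received for T cell activation and IL-6, in a mixed model with "covariates for week (defined as time since initiating placebo/DP), drug (placebo/DP), and their interaction". Nothing similar is planned for adverse events. The as-treated rule in Section 9.5 concerns the primary efficacy analysis through week 12. The monitoring reports in Section 9.7 are pooled over arms or split by arm, not by drug.

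**The concern.** From week 12 the arm label no longer separates DP from placebo. A by-arm safety table that runs past week 12 counts some events that occurred on DP under the arm that began on placebo, and a by-visit test after week 12 no longer has a placebo group. A reader who takes either as DP against placebo could miss a side effect of starting DP. A late test could even make Arm A look safer, simply because Arm B has just begun the drug.

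The timing of side effects bears on this. Section 2.3 says "With long-term use of DP tablets, initial side effects usually disappear". Risk concentrated in the early weeks of treatment is what a by-arm total to week 24 is least able to show, because both arms pass through those weeks on DP.

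There is also unused information. Section 3.0 intends Arm B's weeks 12-24 as DP safety data, but no planned summary presents them as such.

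**Working it through.** The documents give no figure for the safety analysis, so there is none to reproduce. The 80% power in Section 9.4 is for sCD14 and is not affected.

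**Inputs.** 20 subjects per arm (Section 9.4); Arm A takes DP for 24 weeks, Arm B placebo for 12 weeks then DP for 12 (Section 5.1.1); follow-up to week 28 (Section 9.1); visit schedule (Section 6.1).

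**1. What each visit compares.** Post-entry contacts fall at weeks 2, 4, 8, 12, 14, 16, 20, 24 and 28. Weeks 2 and 14 are the calls listed as "Telephone assessment of tolerability/adherence".

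| Weeks | Arm A | Arm B | Contrast |
|---|---|---|---|
| 2, 4, 8, 12 | DP | placebo | DP v placebo |
| 14, 16, 20, 24 | DP, second 12 weeks | DP, first 12 weeks | continuing v new DP use |
| 28 | off drug | off drug | neither on DP |

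After the switch come 5 of 9 contacts, 4 of 7 clinic visits (weeks 4, 8, 12, 16, 20, 24, 28) and 2 of 4 chemistry visits (weeks 4, 12, 16, 24).

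**2. Exposure by label, no dropout.** Arm A: 20 × 24 = 480 DP person-weeks. Arm B: 20 × 12 = 240 placebo and 20 × 12 = 240 DP. DP total: 480 + 240 = 720. Share of DP time under Arm B: 240/720 = 33%.

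**3. What a by-arm total to week 24 estimates.** Let expected events per subject be p on placebo in weeks 0-12, d in the first 12 weeks of DP, and c in the second 12 weeks of DP.

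- Arm A = d + c; Arm B = p + d.
- Arm A − Arm B = c − p. The week 0-12 contrast is d − p.

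This needs no assumed event rate. If side effects fade so that c is close to p, the total shows almost nothing whatever d is. If the rate on DP stays constant at twice the placebo rate, the by-arm ratio is (2 × 24)/(1 × 12 + 2 × 12) = 48/36 = 1.33.

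**4. Conditional illustration.** The documents give no Grade 2 or higher rates, so these 12-week risks are assumptions. Counts are taken as cumulative subjects with at least one event, periods as independent within subject, with 20 per arm. Then Arm A = 1 − (1−d)(1−c) and Arm B = 1 − (1−p)(1−d). For d = 0.40 and p = 0.10, Arm B = 1 − 0.90 × 0.60 = 0.46; Arm A is 0.46 if c = 0.10 and 0.64 if c = 0.40. The week 0-12 difference is 0.30.

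Probability that a two-sided Fisher test gives p < 0.05 with Arm A higher, by exact enumeration:

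| d v p | Week 12 | Week 24, c = p | Week 24, c = d |
|---|---|---|---|
| 40% v 10% | 49% | 1% | 12% |
| 30% v 10% | 24% | 1% | 8% |
| 20% v 10% | 7% | 1% | 4% |

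**5. If visit tests count only new events.** Tests through week 12 are unaffected. For weeks 14-24, spread each 12-week risk evenly over four contacts, so the per-contact risk is 1 − (1 − risk)^(1/4), with contacts independent. With 40% in new users and 10% in continuing users, Arm B is significantly higher in 5% of tests at one contact and in 19% for any of four. With 20% v 10% the figures are 0.2% and 0.9%. Even spread over four contacts cannot hold for laboratory events, which are measured less often.

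**The case against.** The strongest reply is that Section 9.6 never specifies a between-arm comparison of whole-study totals. Its only tests are visit by visit, and those through week 12 are sound. Section 6.3.5 records only new Grade 2 or higher signs and symptoms after entry, which points to new-event counts, at least for clinical events. On that reading step 4 does not arise. This stands: the c − p result and the power losses apply only if by-arm totals to week 24 are reported or visit counts are cumulative. The text leaves that open, and Section 6.3.6 records all Grade 2 or higher laboratory values, not only new ones.

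It is also fair that the higher assumed risks are not anchored in the documents. The four reactions in Table 1 of Section 2.3 sum to 13.6 + 6.1 + 2.3 + 2.3 = 24.3% on DP and 8.2 + 3.5 + 0.0 + 1.1 = 12.8% on placebo, in another population and without a grade restriction. Used as 12-week risks, they give about 8% power at week 12, so there is little power to lose. Nor is a late test wrong in itself: if new users do have more events than continuing users, it detects a real difference. Its fault is that nothing says what it compares.

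A reader might infer that by-arm reporting costs precision for events never seen, since pooling gives 0/40 in place of 0/20. It does not: a by-arm table showing 0/20 and 0/20 already gives 0/40. A reader might also infer that objective 1.3.5 goes unanswered. It does not ask for a placebo comparison, and Arm A's own summary addresses up to 24 weeks of DP.

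None of this supplies a week-12 limit, a label for the later contrasts, or a by-treatment table for Arm B's DP period.

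**Conclusion.** The point holds as a gap in the planned safety analysis. As written, the rule places DP-period events under the placebo-first arm (240 of 720 planned DP person-weeks, without dropout), produces unlabelled DP-versus-DP tests after week 12, and does not present Arm B's weeks 12-24 as the DP safety data that Section 3.0 intends.

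A reader might go further and conclude that the trial has no valid safety comparison with placebo, or that power falls from 49% to between 1% and 12%. The documents support neither. The tests through week 12 are valid, and those power figures rest on assumed risks and cumulative counts that the plan does not state. Late new-event tests would mislead often only if event rates were high.

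The impact is low to moderate: a secondary endpoint in a pilot, with the primary analysis unaffected. The change is worth making because it uses data already being collected.

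**What to change.** Amend Section 9.6 as follows.

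- **Placebo comparison.** Limit the DP-versus-placebo safety comparison to weeks 0-12, before the first period-2 dose. Use subjects with at least one new Grade 2 or higher event, with Fisher's exact test, the risk difference and its confidence interval.
- **Table by treatment received.** Show events and subjects with events for placebo weeks 0-12; the first 12 weeks of DP, for each arm and pooled; DP weeks 12-24 in Arm A; and off drug weeks 24-28. Note that Arm B's DP period has no concurrent placebo group and includes only subjects who reached cross-over.
- **Later visits.** Keep by-visit counts after week 12 as description, labelled as continuing versus new DP use through week 24 and as off drug at week 28. State whether counts are new or cumulative.

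The cost is small: no added visit, sample or subject. Section 6.3.5 requires onset dates for signs and symptoms in source documents; if they are not on the CRF, some must be taken from source. Otherwise assign events by visit interval with the week-12 visit as the cut, which can misplace only events that start between that visit and the first period-2 dose. Laboratory events already carry a visit.

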6.3.5 Clinical Assessments

Complete Physical Examination

A complete physical examination is performed at Screening and is to include at a minimum an examination of the skin, head, mouth, and neck; auscultation of the chest; cardiac exam; abdominal exam; examination of the extremities for edema. The complete physical exam will also include signs and symptoms, diagnoses, height, weight, and vital signs (temperature, pulse, respiration rate, and blood pressure).

Targeted Physical Exam

A targeted physical examination is performed at Entry and all other study visits to include weight and vital signs (temperature, pulse, respiration rate, and blood pressure) and is to be driven by any previously identified or new signs or symptoms, or any diagnoses that the subject has experienced within 30 days prior to entry/since the last visit.

Height

Height will be recorded on the CRF at the screening visit only.

Weight

Weight will be recorded on the CRF at each targeted physical exam.

Signs and Symptoms

At entry, all grades that occurred within 30 days before study entry must be recorded; post-entry, only new signs and symptoms Grade ≥ 2 must be recorded on CRFs. Record on CRFs all signs and symptoms that led to a change in treatment, regardless of grade. The source document must include date of onset and date of resolution.

Diagnoses

After entry, record all HIV-related and AIDS-defining diagnoses (Centers for Disease Control and Prevention [CDC] category B and C), and the following non-HIV diagnoses: diabetes mellitus, dyslipidemia, hypertension, hypotension, MI, coronary artery disease (not MI), congestive heart failure, stroke, malignancy, renal insufficiency, liver disease, pulmonary embolism, deep vein thrombosis, peripheral artery disease (including peripheral artery revascularization), chronic obstructive pulmonary disease (COPD), and asthma.

Each diagnosis must include:

- a) Date of diagnosis, and date of resolution
- b) Method of diagnosis

Concomitant Medications

Record new, or discontinued concomitant medications including immune-based therapy, blinded study treatment, prescription drugs, nonprescription drugs, alternative therapies, and dietary supplements since the last visit.

Study Drug Modifications

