9.2.2 Secondary Endpoints

- Changes from entry to week 12 and 24 (as applicable) in the following:
 - %HLA-DR+ CD38+ expression in CD8+ and CD4+ T-cells
 - %CD69+CD25+ expression in CD4+ and CD8+ T-cells
 - CD16 and tissue factor expression in monocytes
 - Plasma levels of biomarkers of systemic inflammation (sTNF α R, TNF α , hsCRP) and coagulation (D-dimer, tissue factor)
 - Percent brachial artery FMD
 - Proportion of cycling CD4+ and CD8+ T cells as measured by Ki-67 expression
- Grade 2 or higher AEs, treatment discontinuations
- Correlation of plasma DP level to urine adenosine, plasma IL-6, and soluble and cellular markers of immune activation

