9.4 Sample Size and Accrual

There will be 40 subjects (20 per arm) randomized to either DP 100 mg 4 times daily or matching placebo, and it is assumed that no more than 10% of participants will be excluded from the primary analysis due to any reason. sCD14 will be the main primary outcome, while sCD163 and IL-6 will be treated as other key outcomes of interest. As a result, the hypothesis for sCD14 will be tested at the 5% significance level and will be the basis for our power analysis. sCD163 and IL-6 will also be tested at the 5% significance level each. Based on the assumption that none of the 40 subjects are excluded from the primary analysis for any reason, we will have 80% power to detect standardized mean difference of 0.909 between treatment arms for the sCD14. In terms of clinically meaningful effects, this translates to a difference of 0.49×10^6 pg/mL in sCD14 between arms at 12 weeks assuming similar standard deviation seen in preliminary data (standard deviation is 0.54×10^6 pg/mL for sCD14). In the more realistic situation that 10% of subjects are excluded (18 per arm), we will have 80% power to detect standardized mean difference of 0.961 between treatment arms for the primary outcome. In terms of clinically meaningful effects, this translates to a difference of 0.52×10^6 pg/mL in sCD14 between arms at 12 weeks assuming similar standard deviations seen in preliminary data.

Because the ANCOVA model will adjust for baseline sCD14 as well as CD4 cell count (neither of which are expected to be related to treatment arm), it's likely that there will be sufficient power to detect even smaller effects than what is expected.

It is anticipated that subjects will accrue to the study at a rate of 2-3 subjects per month. At this rate, the study should fully accrue within 18 months after the first subject enrolls.

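### Safety is compared between arms only visit by visit: section 9.6 names no per-subject test over the 12 placebo-controlled weeks and does not say how events are counted at a visit

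*Combined protocol and SAP*

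**What the plan says.** Section 9.6 starts with a descriptive summary: "Safety will be evaluated by summarizing the number and frequency of Grade ≥ 2 adverse events within each study arm". It then compares the arms "using Fisher's exact test at each study visit". No other between-arm safety test is named. Each secondary test is at the nominal 5% level: "Statistical significance for each of the secondary analyses will be tested using the nominal 5% type I error rate".

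The endpoint, in section 9.2.2, is "Grade 2 or higher AEs, treatment discontinuations". Section 9.6 describes no between-arm comparison of discontinuations.

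On recording, section 6.3.5 says that "post-entry, only new signs and symptoms Grade ≥ 2 must be recorded on CRFs". Section 6.3.6, by contrast, calls for every Grade 2 or higher laboratory value after entry. Under section 6.2.4, a subject who stops treatment early has a discontinuation visit and is then taken off study.

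Section 9.6 does not say whether the unit is the subject or the event. It also does not say whether a visit's count means events new at that visit, events present at it, or events accumulated up to it.

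**The concern.** Objective 1.3.5 is safety and tolerability. The placebo-controlled evidence ends at week 12, and the natural question is how many subjects on each arm had at least one Grade 2 or higher event by then. The plan never tests that.

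In the schedule of events (section 6.1), clinical assessments before crossover fall at weeks 4, 8 and 12; the week 2 contact is by telephone. If a symptom counts only where it is new, each test sees part of the events. Three features add to this:

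- A subject who leaves for toxicity before week 8 cannot contribute to the week 8 and week 12 tests.
- The visits do not collect the same data. Chemistries are drawn at weeks 4 and 12 but not week 8, and hematology after entry first at week 12.
- A persistent laboratory abnormality may count at several visits, while a persistent symptom counts once.

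A real tolerability difference could therefore go unflagged at every visit.

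**Working it through.** **The plan's own figure.** No power is stated for safety. The only power statement is for sCD14: "we will have 80% power to detect standardized mean difference of 0.909 between treatment arms for the sCD14". With a noncentral t, noncentrality 0.909 × √(20/2) = 2.87, 38 df and two-sided 5%, power is 79.99%, so it reproduces. The second case, 0.961 with 18 per arm, gives 79.98%.

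**Inputs.** From the documents: 20 per arm (section 9.4), 5% per test (section 9.6), three pre-crossover clinic visits (section 6.1). Assumed: the 12-week per-subject event rates and the split of onsets over the visits, since the documents give neither.

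**Step 1: what one visit needs.** With 0 of 20 on placebo and k of 20 on dipyridamole, the two-sided Fisher p is 2 × C(20,k)/C(40,k).

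- k = 4: 2 × 4,845/91,390 = 0.106
- k = 5: 2 × 15,504/658,008 = 0.047

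So at least 5 v 0 subjects at the same visit are needed.

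**Step 2: an example that needs no event rates.** Let 12 of 20 dipyridamole subjects and no placebo subject have a first event, with 4 onsets at each of weeks 4, 8 and 12. Counted at onset, all three visit tests give p = 0.106. The per-subject test of 12 v 0 gives 2 × C(20,12)/C(40,12) = 0.000045.

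**Step 3: power.** For one per-subject test, sum Bin(a; 20, p) × Bin(b; 20, q) over all tables with Fisher p ≤ 0.05. For the visit tests, each subject has an onset at visit j with probability p × w_j and no event with probability 1 − p. Enumerate both multinomials and add up the cases where at least one of the three tables has p ≤ 0.05. All 20 per arm stay in every denominator, so withdrawals are not modelled.

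| Placebo v DP by week 12 | One per-subject test | Any visit, even onset | Any visit, 60/25/15 | Any visit, 80/10/10 |
|---|---|---|---|---|
| 10% v 40% | 49% | 19% | 26% | 36% |
| 10% v 50% | 74% | 36% | 45% | 58% |
| 20% v 60% | 65% | 36% | 39% | 49% |
| 20% v 70% | 85% | 52% | 57% | 69% |

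The relative loss, 1 − (any visit)/(one test), is 38–62% with even onset, 33–47% with 60/25/15 and 18–26% with 80/10/10. For 10% v 50% with even onset it is 1 − 0.364/0.742 = 51%.

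With 18 per arm, 10% v 50% gives 67% against 28% (even) to 51% (80/10/10). For 10% v 40% it is 43% against 14% to 31%.

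**Step 4: the counting rule.** If each visit's count is cumulative, the week-12 test is the per-subject test and nothing is lost. If events carry over to the next visit with probability 0.8, simulation at 10% v 50% gives 68–71% for any significant visit, against 74%. The loss in Step 3 thus depends on onset-only counting. Section 6.3.5 points that way for symptoms, but section 9.6 does not settle it.

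**The case against.** Several points on the other side have force.

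- A reader might infer that by-visit testing cuts power by two thirds or more. That sets one visit's test against the whole alternative, although the plan runs several, and it assumes onset-only counting with evenly spread or constant risk. Section 2.3 says that early side effects tend to fade with longer use, which makes early onset plausible. With 80/10/10 onset at 10% v 50%, week 4 alone has 58% power against 74%. The documents do not support the larger figure as a general statement.
- The assumed rates are large. The only two-arm rates in the documents are for ungraded reactions, such as dizziness at 13.6% v 8.2%. At those rates both approaches have almost no power: 2.8% for the per-subject test and 0.1% for a single visit.
- A reader might also infer an inflated false-positive rate, since three independent 5% tests give 1 − 0.95³ = 14.3%. That is an upper bound. Fisher's test is conservative here, with an actual size of about 2.4% or less per test at the rates checked.
- By-arm safety information is not missing. Section 9.6 summarizes frequencies by arm, and section 9.7 provides quarterly by-arm reports and monitoring-board review.
- Objective 1.3.5 asks to evaluate safety for up to 24 weeks. It does not literally ask for a 12-week between-arm test.

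These points limit the size of the concern. They do not supply a per-subject between-arm comparison or a counting rule.

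**Conclusion.** The concern holds as a gap in the analysis plan with an uncertain, assumption-dependent cost. The only between-arm safety test is by visit. The unit and counting rule are undefined, and the per-subject comparison over the placebo-controlled period is absent.

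If each event counts once at onset, the chance of any significant visit is about 18–62% lower, in relative terms, than the power of one per-subject test. That range covers the four assumed rate pairs and three onset patterns with 20 per arm. With strong carry-over the loss is small, and under cumulative counting week 12 loses nothing. The calculation leaves out the further loss when early toxicity withdrawals drop from later visits.

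This does not make the safety data uninformative, and the per-subject test is not well powered either: 49% at 10% v 40%. Under either analysis, a non-significant result should not be read as showing tolerability.

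**What to change.** In section 9.6, make the between-arm safety comparison the number of subjects with at least one new Grade 2 or higher adverse event from first dose to the week-12 visit. Use Fisher's exact test and report the risk difference with an exact 95% CI. Do the same for treatment discontinuation, which section 9.2.2 already lists. Counting from first dose keeps subjects who withdraw early in the comparison.

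Keep the by-visit counts as a descriptive table and state its counting rule: subjects or events; new, present or cumulative; and how a laboratory abnormality that persists across visits is handled. Add a sentence that a non-significant difference is not evidence of tolerability at this sample size, so that the interval carries the interpretation.

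The cost is a wording change on data already collected. What is lost is formal p-values for the timing of events; the descriptive table still shows the timing.
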